### **6.1.4. Imputation of Missing Data**

Missing viral load data due to premature discontinuation of the study will not be imputed as all available data will be included in the time-weighted average calculations. Intermediate missing viral load data will be imputed using the trapezoidal rule for the time-weighted average calculations.

## **6.2. Secondary Efficacy Endpoints**

### **6.2.1. Definition of Secondary Efficacy Endpoints**

The secondary efficacy endpoints of this study are as follows:

- Time-weighted average change in FLU-PRO score from Day 1/Baseline through Day 7
- Percent change from study baseline in FEV1% predicted value at Day 28/End of Study

The FLU-PRO score will be calculated as the sum of the scores for all symptoms collected divided by number of symptoms with the non-missing score (ie, the number of symptoms collected).

FEV1 % predicted value is calculated as a percent of the 'predicted values' for the patients of similar characteristics (height, age, sex, and sometimes race and weight). The method based on {[Hankinson 1999](#)} (aka NHANES III, 1999) will be used to calculate the FEV1 % predicted value.

### **6.2.2. Analysis Methods for Secondary Efficacy Endpoints**

The FAS analysis set will be used for all summaries and analyses of the secondary endpoints.

The treatment difference in the time-weighted average change in FLU-PRO score from Day 1/Baseline to Day 7 will be analyzed using an ANCOVA model with the baseline FLU-PRO score and stratification factors as covariates.

The treatment difference in the percent change from study baseline in FEV1 % predicted value at Day 28 will be analyzed using an ANCOVA model with the study baseline FEV1 % predicted value and stratification factors as covariates. The study baseline FEV1 % predicted value is defined as the lowest FEV1 % predicted value collected on or prior to the first dosing date if multiple non-missing numeric assessments exist. The data collected on eCRF will be used for the analyses.

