6.7.13. Spirometry

Spirometry testing measurements, obtained by certified respiratory therapists or other nurses/technicians trained in pulmonary function testing, will be obtained at Screening or on Day 1/Baseline and Day 28/End of Study.

The study Day 1/Baseline forced expiratory volume in 1 second (FEV₁) and forced vital capacity (FVC) but must be obtained *prior to IMP administration*. Alternatively, measures of FEV₁ and FVC obtained for the purposes of patient care within 2 days prior to Day 1/Baseline may be used to satisfy the Screening/Day 1/Baseline spirometry measurements. However, these tests must have been obtained at the local site of subject enrollment and the same spirometry machine should be utilized for the Day 28/End of Study measurement.

The Day 28/End of Study spirometry measurements by the certified respiratory therapist do not have to be obtained the same day as the clinic visit, but must be performed within the study visit window (+2 days). Spirometry measures performed as part of standard clinical care within the visit window will be acceptable.

Subjects will also be issued a handheld spirometer for self-administered spirometry testing. These handheld spirometry measures will be obtained by the subject at Days 1/Baseline, 3, 5, 7, 9, 14, 21, and 28/End of Study. Handheld spirometry measures must be obtained in the presence of study staff at Days 1/Baseline and 28/End of Study.

In addition to the study-specific measures described above, all spirometry and other measurements of pulmonary function obtained at unplanned study times, as part of standard clinical care during the study period, will be collected.

Finally, historical spirometry test values will also be collected as follows:

- 1) the average of the 2 highest FEV₁ values and 2 highest PEF_{25%-75%} values measured post-lung transplant, obtained at least 3 weeks apart without the administration of a bronchodilator (the “baseline” values used as a reference point for any future diagnosis of bronchiolitis obliterans syndrome [BOS]), and

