### **3.8.3. Selection of Data in the Event of Multiple Records**

Depending on the statistical analysis method, single values may be required for each analysis visit. If multiple valid, nonmissing, continuous measurements exist in an analysis window, records will be chosen based on the following rules if a single value is needed:

- In general, the baseline value will be the last nonmissing value on or prior to the first dosing date of study drug, unless specified differently. If multiple measurements occur on the same day, the last nonmissing value prior to the time of first dosing of study drug will be considered as the baseline value. If these multiple measurements occur at the same time or the time is not available, the average of these measurements (for continuous data) will be considered the baseline value. For the efficacy endpoints, if no measurements occur prior to the time of first dosing of study drug, the first nonmissing value on the first dose date of study drug will be considered as the baseline value.
- For postbaseline values:
  - The record closest to the nominal day for that visit will be selected.
  - If there are 2 records that are equidistant from the nominal day, the later record will be selected.
  - If there is more than 1 record on the selected day, the average will be taken, unless otherwise specified.

If multiple valid, non-missing, categorical measurements exist for one visit, records will be chosen based on the following rules if a single value is needed:

- For baseline, the last available record on or prior to the date of the first dose of study drug will be selected. If there are multiple records at the same time or no time recorded on the same day, the value with the lowest severity will be selected unless otherwise specified.
- For postbaseline values:
  - The record closest to the nominal day for that visit will be selected.
  - If there are 2 records that are equidistant from the nominal day, the later record will be selected.
  - If there is more than 1 record on the selected day, the value with the worst severity will be used.

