### 6.2.4. Imputation of Missing Data

Missing FLU-PRO data due to premature discontinuation of the study will not be imputed as all available data will be included in the time-weighted average calculations. Intermediate missing FLU-PRO data will be imputed using the trapezoidal rule for the time-weighted average calculations.

Missing FEV1 % predicted value will not be imputed given only 2 assessments are used for analysis (ie, data collected at study baseline and Day 28 visit).

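### Taking the lowest pre-dose FEV1 % predicted as study baseline inflates the reported within-arm percent change at Day 28; the randomized comparison stays valid

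*SAP*

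**What the plan says.** SAP 6.2.2 analyses percent change in FEV1 % predicted at Day 28 by ANCOVA, with study baseline and the stratification factors as covariates. The baseline % "predicted value is defined as the lowest" value "collected on or prior to the first dosing date if multiple non-missing numeric assessments exist".

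Day 28 follows the general postbaseline rule in SAP 3.8.3: "The record closest to the nominal day for that visit will be selected", with the later record taken if two are equidistant and an average if several fall on the chosen day. SAP 6.2.4 confirms that no other values enter, "given only 2 assessments are used for analysis".

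The SAP's general baseline rule is different but allows exceptions: "the baseline value will be the last nonmissing value on or prior to the first dosing date of study drug, unless specified differently".

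Protocol 3.1 and 8.1.3 define the endpoint as change from Day 1 or study baseline. Protocol 6.7.13 requires that reading before dosing and allows care tests "within 2 days prior to Day 1/Baseline may be used to satisfy the Screening/Day 1/Baseline spirometry measurements". It contains no lowest-value rule. SAP 6.2.3 plans one FEV1 sensitivity analysis, in the Per Protocol set. None uses another baseline.

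**The concern.** The minimum of several noisy readings lies below the subject's true level on average, and further below it the more readings there are. The Day 28 value has no matching selection. Percent change from the minimum is therefore positive on average in a subject whose lung function is stable.

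What is at stake is the reported FEV1 recovery within each arm in Table 15.9.2.2.1, and presumably in Figure 15.9.2.2.2. Anyone who reads one arm alone, or compares it with an outside series, would see recovery that partly reflects the baseline rule.

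The wording raises a second point. The sentence has no earliest date, and it limits by dosing date rather than dosing time. Taken literally, it admits values older than the protocol's window and readings taken later on Day 1 after the dose.

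**Working it through.** The documents give no SD, effect size or power for FEV1, so there is no planned figure to reproduce. The error sizes below are assumptions.

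**1. Size within a subject, no true change.** Set the true level to 1 and let each reading have independent normal error with CV *c*. For the minimum of *k* readings, the expected shortfall is *m·c* and the variance is *v·c²*:

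- k = 1: m = 0, v = 1
- k = 2: m = 1/√π = 0.5642, v = 1 − 1/π = 0.6817
- k = 3: m = 3/(2√π) = 0.8463, v = 1 + √3/(2π) − 9/(4π) = 0.5595

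Mean percent change ≈ 100 × { [1/(1 − mc)] × [1 + vc²/(1 − mc)²] − 1 }.

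At c = 0.05:

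- k = 1: 1 + 0.0025 − 1 gives +0.25%, about +0.3%
- k = 2: 1/0.97179 = 1.02903; 0.6817 × 0.0025/0.97179² = 0.00180; product 1.0309, so +3.1%
- k = 3: 1/0.957685 = 1.04418; 0.5595 × 0.0025/0.957685² = 0.00153; product 1.0458, so +4.6%

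| Pre-dose values | CV 3% | CV 5% | CV 8% |
|---|---|---|---|
| 1 | +0.1 | +0.3 | +0.6 |
| 2 | +1.8 | +3.1 | +5.2 |
| 3 | +2.7 | +4.6 | +7.7 |

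A Monte Carlo run of 400,000 draws agrees.

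**2. Size in an arm.** This is a weighted mean over the number of readings per subject, which the documents do not give. Two assumed splits for 1/2/3 readings, at CV 5%:

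- 80/15/5%: 0.80 × 0.3 + 0.15 × 3.1 + 0.05 × 4.6 = +0.9%
- 50/30/20%: 0.50 × 0.3 + 0.30 × 3.1 + 0.20 × 4.6 = +2.0%

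The reference, if every subject has one reading, is +0.3%.

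**3. Treatment difference.** The planned ANCOVA was simulated with 34 and 17 subjects (SAP 1.3) at two-sided 0.04 (Protocol 8.5.2), strata omitted, 4,000 runs per case. Assumptions: true mean 60% predicted, between-subject SD 15, within-subject SD 2, 4 or 6 points, one to three pre-dose values. This error model is additive, so its within-arm figures differ from step 1.

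Results with no true change and within-subject SD 4:

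| Baseline rule, values | Presatovir | Placebo | Adjusted difference | Rejection rate |
|---|---|---|---|---|
| Lowest of 2 | +4.61 | +4.57 | +0.03 | 0.036 |
| Last of 2 | +0.52 | +0.49 | +0.03 | 0.039 |
| Lowest of 3 | +6.81 | +6.81 | +0.01 | 0.040 |
| Last of 3 | +0.54 | +0.55 | −0.01 | 0.042 |

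Over all cases and both rules, the adjusted difference lies between −0.02 and +0.07, within Monte Carlo error of zero. Rejection lies between 0.036 and 0.045. The Monte Carlo SE of a 0.04 rate is √(0.04 × 0.96/4000) = 0.003.

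With a true 8% relative effect, SD 4 and two values, the estimate is 8.40 under the lowest-value rule and 8.07 under the last-value rule. The smaller denominator enlarges it by 0.33 points.

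**The case against.** **The tested result is protected.** This stands. Baseline assessments precede randomization (Protocol 6.1.2.2), so the artefact is equal in expectation in both arms. A reader might infer a false treatment effect or a noisier comparison. Step 3 supports neither: with two values at SD 4, the SD of the estimated difference is 3.03 under the lowest-value rule and 3.06 under the last-value rule. With the 50/30/20 split it is 3.19 against 3.12.

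**One pre-dose reading is the usual case.** This largely stands. Protocol 6.7.13 asks for on-site spirometry at Screening or Day 1. Protocol 6.1.2.1 requires it on Day 1 only if none was done in the preceding 2 days, and the Screening list in 6.1.1 omits it. However, the Appendix 2 grid marks both columns, and the SAP sentence itself provides for multiples.

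**The SAP is not in conflict with itself.** This stands. A reader might say that 6.2.2 improperly overrides 3.8.3, but 3.8.3 allows differently specified baselines. The protocol's 2-day provision says which tests may serve, not how to choose among several. SAP 6.5, where departures from the protocol would be listed, is redacted, so the change cannot be called undeclared.

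**The open look-back matters little in practice.** This is partly right. Section 6.2.2 is confined to eCRF data, and the listings separate historical (16.2.6.4) and handheld (16.2.6.11) spirometry from the clinical-database values. The historical values collected under Protocol 6.7.13 are mainly the highest ones and would seldom be the minimum. These limits are implied rather than stated.

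**Differences between pre-dose readings may be real.** Subjects have new or worsening symptoms within 7 days, so a low reading may be a true low point. Even so, change from a low point is not change from the Day 1 or study baseline that the protocol names.

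**Table 15.9.3.5 (drops of at least 10%).** A reader might infer that it would miss decliners. Its methods are redacted and its baseline is unknown. It also covers FEV1 or FVC, on absolute and % predicted scales. No such claim can be made.

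**Conclusion.** The concern holds for descriptive, within-arm FEV1 change. In a subject with two pre-dose readings, the rule adds an apparent gain of about 3 percentage points, and with three about 4 to 5, if the within-subject CV is 5% and the readings scatter around a stable level. The CV is assumed, and the 3-8% range gives mean changes from +1.8% to +7.7%. With one reading there is no effect from the rule. The arm-level inflation cannot be fixed from the documents; under the two assumed splits the arm mean is +0.9% or +2.0%, against +0.3%.

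It does not hold for the hypothesis test. With no true effect, the adjusted difference is unbiased and the error rate stays at its nominal level. A true effect is slightly enlarged. That conclusion assumes that the values used precede randomization, which the SAP wording should secure by excluding readings taken after dosing.

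**What to change.** Replace the sentence in SAP 6.2.2. Define study-baseline FEV1 % predicted as the last on-site, non-handheld value before the first dose within the protocol's Screening/Day 1 window, including care tests within 2 days before Day 1. Average same-day values only when their times are identical or missing, as SAP 3.8.3 does for baseline.

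If the lowest-value rule is kept, state the reason, give it a start date and a pre-dose time limit, and add a sensitivity analysis with the last pre-dose value. In either case, report how many subjects per arm had more than one qualifying value.

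The cost is one SAP sentence and one derivation change, plus one extra table if the rule is kept. No new data are needed. The change should be made before the blind is broken.

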### 6.2.3. Sensitivity Analysis for Secondary Efficacy Endpoints

The following sensitivity analyses will be performed:

- Percent change from study baseline in FEV1 % predicted value at Day 28 will be analyzed in the PP analysis set.
- Time-weighted average change in FLU-PRO will be analyzed in the PP analysis set.
- Time-weighted average change in FLU-PRO will be analyzed for subjects in FAS who have at least one postbaseline FLU-PRO data through Day 7.

### 6.2.4. Imputation of Missing Data

Missing FLU-PRO data due to premature discontinuation of the study will not be imputed as all available data will be included in the time-weighted average calculations. Intermediate missing FLU-PRO data will be imputed using the trapezoidal rule for the time-weighted average calculations.

Missing FEV1 % predicted value will not be imputed given only 2 assessments are used for analysis (ie, data collected at study baseline and Day 28 visit).

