1. INTRODUCTION

1.1. Background

Respiratory syncytial virus (RSV), a member of the family *Paramyxoviridae*, is an enveloped virus with a negative single-strand ribonucleic acid (RNA) genome. The RSV genome encodes 11 proteins, including 3 surface glycoproteins (F, G, and SH) and several proteins that comprise the viral RNA polymerase complex (N, P, L, and M2-1). Two major antigenic subgroups of RSV are known, RSV A and RSV B, that differ primarily in the genetic sequence of the G glycoprotein while maintaining a higher degree of homology across other parts of the genome. Both subgroups show comparable pathogenicity and can co-circulate in the same community during a seasonal epidemic, but their individual prevalence usually varies from season to season.

While RSV infection is commonly recognized as an important virus affecting pediatric patients, it is also an important cause of respiratory disease in the adult population. Those at particular risk include immunosuppressed adults, such as recipients of a solid organ transplant, especially those with a lung transplant (LT). Each winter, up to 12% of LT patients are infected with RSV {[Federman 2003](#)}, {[Weinberg et al 2010](#)} resulting in a mortality rate as high as 10% to 20% {[Palmer et al 1998](#)}, {[McCurdy et al 2003](#)}, {[Hopkins et al 2008](#)}. Respiratory viral infections, including RSV, are associated with the development of chronic lung allograft dysfunction (CLAD), the most recognized form being bronchiolitis obliterans syndrome (BOS) {[Vu et al 2011](#)}, {[Khalifah et al 2004](#)}. Multiple studies suggest the incidence of BOS is higher after a respiratory viral infection, with RSV specifically implicated {[Federman 2003](#)}, {[Khalifah et al 2004](#)}, {[Bridges et al 1998](#)}, {[Palmer et al 1998](#)}, {[Hayes et al 2012](#)}, {[Hopkins et al 2008](#)}. It is hypothesized that these viral infections lead to graft rejection through the triggering of an alloreactive immune response against tissue antigens {[Koehn et al 2006](#)}. BOS is of particular concern as it carries a substantial associated morbidity and mortality in LT patients.

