### **3.1.3. Per Protocol Analysis Set**

The Per-Protocol (PP) Analysis Set includes subjects in the FAS who meet the following criteria:

- Did not violate the following major exclusion criteria (EC)
  - EC #2: Use of a strong or moderate cytochrome P450 enzyme (CYP) inducer within 2 weeks prior to drug dosing
  - EC #16: An estimated eGFR  $<30$  mL/min/1.73m^2 obtained  $\leq 7$  days prior to Screening
  - EC #17: ALT or AST  $> 5$  times the ULN obtained  $\leq 7$  days prior to Screening
  - EC #18: Clinically significant elevations in total bilirubin (TB)
- Did not violate the following major inclusion criteria (IC)
  - IC #3: Had new onset respiratory symptoms or acute worsening of chronic preexisting symptoms  $\leq 7$  days prior to IMP administration on Day 1/Baseline
- Missed  $\leq 2$  doses (4 tablets) over the course of treatment
- Missed  $< 3$  nasal swab samples over the course of the study

The PP Analysis Set is the secondary analysis set for efficacy analyses.

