#### 6.1.2. Analysis for the Co-Primary Efficacy Endpoints

The co-primary analyses will test the 2 null hypotheses in the following sequence:

- $H_{01}$ : There is no difference between presatovir and placebo in the time-weighted average change in RSV  $\log_{10}$  viral load from Day 1 to Day 7 in the FAS
- $H_{02}$ : There is no difference between presatovir and placebo in the time-weighted average change in RSV  $\log_{10}$  viral load from Day 1 to Day 7 in the FAS with whose duration of RSV symptoms prior to the first dosing date of study medication is  $\leq$  median of the symptom duration distribution in the overall FAS population

To test the null hypothesis above, a parametric analysis of covariance (ANCOVA) model with corresponding baseline viral load and stratification factors (treatment of RSV infection with ribavirin and use of palivizumab or IVIG) as covariates will be used, at a 2-sided 0.05 level. Adjusted means and 95% confidence intervals (CIs) will be provided. The stratified Wilcoxon rank sum test will be implemented as a sensitivity analysis. The tests will be 2-sided with significance levels specified in Section 3.5.

Viral load values below the limit of detection (LOD) will be assigned as 0 if it is reported in the form of 'not detected'. A value of 1 unit less than the LOQ will be used for analysis if the viral load is reported in the form of "< x" (where x is considered the LOQ). Viral load data will be transformed using the base 10 logarithm for the analyses and summaries. To account for 0 values, 1 will be added to each viral load measurement before being transformed.

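### The Day 28 FEV1 test and its only listed sensitivity analysis are both complete-case, with no stated handling of subjects who died or were ventilated

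*SAP*

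**What the plan says.** - **Place in the testing order.** Protocol 8.5.2 and SAP 3.5 test two secondary endpoints in sequence after the primary hypothesis is rejected: FLU-PRO first, then percent change in FEV1 % predicted at Day 28. The alpha is 0.04 in the FAS and 0.017 in the short-symptom-duration subgroup.
- **Main analysis.** SAP 6.2.2: "The FAS analysis set will be used for all summaries and analyses of the secondary endpoints". The percent change in FEV1 % "predicted value at Day 28 will be analyzed using an ANCOVA model with the study baseline" value and the stratification factors as covariates.
- **Missing values.** SAP 6.2.4 says that a missing FEV1 % predicted "value will not be imputed given only 2 assessments are used for analysis", the two being study baseline and Day 28.
- **Sensitivity analysis.** SAP 6.2.3 lists one for FEV1: the percent change in FEV1 % "predicted value at Day 28 will be analyzed in the PP analysis set". FLU-PRO has that and a second one within the FAS.
- **Per-protocol set.** SAP 3.1.3 requires, among other criteria, at most 2 missed doses and fewer than 3 missed "nasal swab samples over the course of the study".
- **Promise in the protocol.** Protocol 8.3 expects little missing data and leaves to the SAP the handling of data missing through discontinuation or other reasons.
- **Background risk.** Protocol 1.1 describes RSV infection in lung transplant recipients as "resulting in a mortality rate as high as 10% to 20" per cent.

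**The concern.** A subject who has died or is on a ventilator at Day 28 has no spirometry value because of a bad outcome, often a bad lung outcome. Leaving that subject out means that the comparison is made among those well enough to blow. If presatovir prevents deterioration, the placebo subjects who would show it drop out of the FEV1 comparison. If presatovir causes deterioration, the presatovir subjects who would show it drop out.

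The reason given for not imputing, that only two assessments are used, describes the analysis and not what is known. Death and its date are collected (Protocol 6.7.8), mechanical ventilation is listed (SAP 13.3), and handheld spirometry is scheduled on eight days (Protocol 6.7.13). At stake is how far a positive or null result for the one gatekept lung measure can be relied on.

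**Working it through.** **1. The plan's own figures.** The documents give no power or sample size for FEV1. The general figures reproduce: 51 / 0.85 = 60 randomised. With 34 v 17, a 1.2 log difference, SD 1.2 and 2-sided 0.04, primary-endpoint power is 89% (noncentral t) to 91% (normal), against the stated minimum of 85%. I use 34 v 17 and 0.04 below.

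**2. Can the per-protocol analysis help?** Swabs are due on Days 1, 3, 5, 7, 9, 14, 21 and 28. If swabs not taken because of death count as missed, a death before the Day 14 visit means 3 missed (Days 14, 21, 28), so the subject leaves the set. A death between Days 14 and 21 means 2 missed, so the subject can stay in, but still has no Day 28 FEV1. The per-protocol analysis restores nobody.

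**3. How many subjects?** Taking the protocol's literature range at face value, as an upper bound and not a forecast: 0.10 × 51 = 5.1 to 0.20 × 51 = 10.2 overall, and 0.10 × 17 = 1.7 to 0.20 × 17 = 3.4 on placebo.

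**4. Size of the bias.** Assumptions, none from the documents: SD of percent change 15 points; completer difference d; affected subjects D = 25 points worse than completers; affected fractions p(placebo) and p(presatovir). A dead subject has no FEV1, so D only stands in for the severity of the outcome.

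- Complete-case difference = d
- Difference with everyone counted = d + D × (p(placebo) − p(presatovir))

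Power is from simulation (5,000 to 6,000 trials per scenario), using a t test in place of the ANCOVA and an unstratified Wilcoxon with worst rank for the affected.

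| Affected, placebo / presatovir | d | Everyone counted | Power, complete-case | Power, worst-rank |
|---|---|---|---|---|
| 20% / 5% | 5 | 5 + 25 × 0.15 = 8.75 | 16% | 36% |
| 10% / 3% | 5 | 5 + 25 × 0.07 = 6.75 | 16% | 23% |
| 10% / 10% | 5 | 5.0 | 16% | 12% |
| 20% / 20% | 5 | 5.0 | 14% | 8% |
| 5% / 20% (harm) | 0 | 0 − 25 × 0.15 = −3.75 | – | – |

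The simulated differences agree with the formula to about 0.2 points.

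**5. A second loss model.** Suppose there is no true difference and the lowest values in each arm are the missing ones. The observed mean then rises by SD × φ(z) / (1 − q), where q is the fraction lost and z its normal quantile.

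- q = 0.20: 15 × 0.280 / 0.80 = 5.25
- q = 0.10: 15 × 0.1755 / 0.90 = 2.93

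With 20% lost on placebo and 10% on presatovir, the difference is 2.93 − 5.25 = −2.3 points against presatovir (simulation: −2.4), and the nominal 0.04 test rejects about 6% of the time. Reversing the loss gives +2.3 in favour of presatovir and about 8%. Equal loss of 10% or 20% gives no shift and about 4%.

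**The case against.** The strongest reply is that these losses may be few, that the most severe outcomes are reported elsewhere, and that how to handle death is a matter of choice.

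- **Few losses.** Protocol 4.3 excludes invasive ventilation, shock needing vasopressors, BOS Stage 3 and rapidly deteriorating lung function, and Protocol 8.3 expects minimal missing data. The literature mortality has no stated 28-day window. This stands as a reason to expect lower rates than 10% to 20%. It does not remove the point, because with about 17 placebo subjects one or two losses are 6% to 12% of the arm.
- **Other analyses exist.** A reader might infer that the worst lung outcomes never enter any FEV1 test. The documents do not support that. Severe declines measured at Day 28 are in the ANCOVA. SAP 13.1 lists a FAS table of a 10% or greater drop in FEV1 or FVC by Day 28 (15.9.3.5), and the SAP's exploratory methods are blacked out in the public copy. SAP 3.8.2 also assigns early-termination data to the next scheduled visit. Whether that yields an FEV1 value is unclear: Protocol 6.5.2 names handheld spirometry only, the procedures table marks spirometry at early termination, and SAP 13.3 lists handheld data separately. It cannot help for a subject who dies without a termination visit.
- **Not the only lung measure.** FVC change, respiratory failure needing ventilation and ventilator-free days also have FAS tables. FEV1 is the only gatekept one.
- **Harm would still be seen.** Deaths, SAEs and severe AEs are summarised by arm (SAP 7.1.6). The bias affects the FEV1 result, not the visibility of harm in the trial as a whole.
- **The per-protocol set.** It might be read as removing still more of these subjects. It does not: they are already absent from the FAS ANCOVA. It simply does not help.
- **Choice of method.** Multiple imputation, tipping-point or composite analyses are alternatives. The Wilcoxon test for the primary endpoint (SAP 6.1.2: "The stratified Wilcoxon rank sum test will be implemented as a sensitivity analysis") is no precedent for handling death; it shows only that the test is already in the plan. Since the ANCOVA is left unchanged, the proposal does not settle the choice of main method.

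**Conclusion.** The point holds as a gap in robustness. The only gatekept lung-function test, and the only sensitivity analysis listed for it, are complete-case, and no visible rule covers subjects with no Day 28 value because of death or ventilation.

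The consequence is conditional. If losses differ by arm, the FEV1 difference is biased in either direction: 5.0 v 8.8 points at 20% placebo and 5% presatovir affected, and 0 v −3.75 points when the imbalance is reversed and completers do not differ. With equal loss there is no bias. These sizes rest on an assumed SD of 15, an assumed 25-point deficit and assumed loss rates.

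It might also be inferred that a worst-rank test would be more powerful. That is true only when placebo loses clearly more subjects; with equal loss it is weaker (12% v 16%, 8% v 14%). The case for adding it is bias and robustness, not power, which is why it belongs as a sensitivity analysis. This is a cheap improvement, not a flaw that invalidates the main analysis.

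**What to change.** Keep the ANCOVA as the main analysis. In SAP 6.2.3 add:

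1. A FAS sensitivity analysis of percent change in FEV1 % predicted by stratified Wilcoxon test. Subjects with no Day 28 spirometry who are recorded as having died by Day 28, or as being on mechanical ventilation at the Day 28 visit, receive the worst rank.
2. Beside the ANCOVA result, the number per arm with missing Day 28 FEV1, split into death, ventilation and other.

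Define the worst-rank group by recorded death or ventilation and not by a reason for missing spirometry. The documents show no field for such a reason; only the oxygen saturation assessment (Protocol 6.7.5.1) asks for one.

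Cost: SAP wording and one table, with no new data. The rank analysis gives no estimate in percentage points, and it has less power than the complete-case test if losses are equal between arms.
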